4.3.1.2.3. Annualized Rate of Hospitalization for EGPA-related Events

Endpoint
Annualized rate (event/year) of hospitalization for EGPA-related events

Model Specification

The annualized rate of hospitalization for EGPA-related events will be analyzed by using a negative binomial generalized linear model with logarithm of time as an offset variable, without covariate. The annualized rate and associated 95% CIs will be calculated by exponential transform the value of intercept term and associated 95% CIs estimated when the above model was applied. The annualized rate will be calculated in observation period and retrospective period independently.

Terms in the model:

- **Response**: number of recorded, on-treatment, hospitalization for EGPA-related events experienced per participant.
- Offset: logarithm of treatment time in year

Observation period:

Treatment time in year for each participant will be calculated as:

Participants who complete the study:

 $\{(date of end of Nucala - date of start of Nucala) + 1\} / 365.25$

Participants who enter the follow-up period:

 $\{(date of end of Nucala + 28 - date of start of Nucala) + 1\} / 365.25$

For the raw value of calculation result, round off to two decimal places will be applied.

If the date of end of Nucala is missing, the date of start of the last administration of Nucala + 28 days will be imputed for the date of end of Nucala.

```
Retrospective period:
```

Treatment time in year for each participant will be calculated as:

48 / 52

```
SAS code:
```

```
proc genmod data = <dataset>;
  model n_hosp =
  / link=log dist=negbin offset=logfuinyears;
run;
data parm_est(keep= val rate rate_ll rate_ul);
  set out_parm(where=(parameter='Intercept'));
  format rate rate_ll rate_ul 8.2;
  val= "annualized rate of hospitalization for EGPA-related events
from negative binomial model without covariate";
  rate=exp(estimate);
  rate_ll=exp(lowerwaldcl);
  rate_ul=exp(upperwaldcl);
  run;
```

where n_hosp is the number of hospitalizations for EGPA-related events per participant in follow-up time, and logfuinyears is logarithm of the treatment time in years.

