4.3.1.2.4. Annualized Rate of Emergency Room/Unscheduled Visit for EGPArelated Events

Endpoint

Annualized rate (event/year) of emergency room/unscheduled visit for EGPA-related events

Model Specification

The annualized rate of emergency room/unscheduled visit for EGPA-related events will be analyzed by using a negative binomial generalized linear model with logarithm of time as an offset variable, without covariate. The annualized rate and associated 95% CIs will be calculated by exponential transform the value of intercept term and associated 95% CIs estimated when the above model was applied. The annualized rate will be calculated in observation period and retrospective period independently.

Terms in the model:

- **Response**: number of recorded, on-treatment, emergency room/unscheduled visit for EGPA-related events experienced per participant.
- **Offset**: logarithm of treatment time in year

Observation period:

Treatment time in year for each participant will be calculated as:

Participants who complete the study:

{(date of end of Nucala – date of start of Nucala) + 1} / 365.25

Participants who enter follow-up period:

 $\{(date of end of Nucala + 28 - date of start of Nucala) + 1\} / 365.25$

For the raw value of calculation result, round off to two decimal places will be applied.

If the date of end of Nucala is missing, the date of start of the last administration of Nucala + 28 days will be imputed for the date of end of Nucala.

Retrospective period:

Treatment time in year for each participant will be calculated as:

48 / 52

SAS code:

proc genmod data = <dataset>;

```
model n_emv =
/ link=log dist=negbin offset=logfuinyears;
run;

data parm_est(keep= val rate rate_ll rate_ul);
set out_parm(where=(parameter='Intercept'));
format rate rate_ll rate_ul 8.2;
val= "annualized rate of emergency room/unscheduled visit for
EGPA-related events from negative binomial model without
covariate";
rate=exp(estimate);
rate_ll=exp(lowerwaldcl);
run;
```

where n_emv is the number of emergency room/unscheduled visit for EGPA-related events per participant in follow-up time, and logfuinyears is logarithm of the treatment time in years.

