6.1.1. Participant Disposition

A summary of the number and percentage of participants who completed the study as well as those who prematurely withdrew from the study and screening failure will be provided. Reasons for study withdrawal and screening failure will also be summarized and listed. Those who have discontinued Nucala treatment but not withdrawn from study will be categorized as study completion. Screen failure summary will be based on the screened population.

The number and percentage of participants who completed Nucala treatment as well as the number who discontinued Nucala treatment prior to the end of the study will be summarized, along with the reasons for discontinuation of Nucala treatment, and these will also be listed for the TP population.

The number and percentage of participants who entered in the observation period and in the follow-up period will be summarized. Participants who have discontinued the treatment of Nucala on or after the first treatment discontinuation +29 days are defined as the participants in the follow-up period.

Туре	Definitions
Study completion	A participant completed the observation period, which is scheduled for 96 weeks (approximately 2 years) at maximum.
Early withdrawal	A participant who was enrolled to this study but withdrew during the observation period.
Screening failure	A participant who consented to participate in the study but did not meet the eligibility criteria at Screening.

Study completion, early withdrawal and screening failure are defined as follows.

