6.2.2. Study Period

Assessments and events will be classified according to the time of occurrence relative to the study period.

Screening period is defined as 0-4 weeks before the date of dose of Nucala at Week 0.

Observation period is defined as time from the date of dose of Nucala at Week 0 to the stop date of Nucala +28 days for the participants who did not withdraw from study, or the first treatment discontinuation date +28 days for the participants who withdraw from study. If the date of dose of Nucala at Week 0 is missing, the latest available date between the screening visit date and the Week 0 visit date will be used for the start date of the observation period. When the last Nucala stop date is missing, the last Nucala start date will be imputed.

Follow-up period is defined as time from the first treatment discontinuation date +29 days to 96 weeks within the observation period at maximum. The follow-up period is only applicable for the participants who discontinued the treatment.

Retrospective period is defined as time (within 12 weeks) before the first dose of Nucala. For data of hospitalization for EGPA-related events and ER/Unscheduled visit for EGPA-related events the period is defined as time (within 48 weeks) before the first dose of Nucala.

The study periods to use for summaries on each endpoint are as below.

A:	PMS period	B: Observation period
Retrospective		
period		

Participants who completed the study

Participants who discontinued and moved to the follow-up period

C:	PMS period	D: Observation	E: Follow-up
Retrospective		period	period
period			

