6.2.3. Study Day and Nucala Stop Date

The study day will be calculated relative to visit date of Week 0 and as the number of days from Week 0:

- Ref Date = Missing then Study Day = Missing
- Ref Date < Week 0 then Study Day = Ref Date Week 0
- Ref Date \geq Week 0 then Study Day = Ref Date (Week 0) + 1

The duration of exposure to Nucala is calculated as (Nucala stop date – Nucala start date + 29). If overall Nucala stop date is missing, the last Nucala start date will be imputed.

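### The person-time offset for the two annualized rates does not match the observation period in SAP 6.2.2, and early withdrawals have no formula

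*SAP*

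**What the plan says.** SAP 4.3.1.2.3 (hospitalization) and 4.3.1.2.4 (emergency room or unscheduled visits) each fit an intercept-only negative binomial model with log treatment time as offset. Both state that the rate is obtained for the observation period. SAP 4.3.1.2 makes the Treated Population (TP) the analysis set.

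Both sections give two formulas for treatment time:

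- Participants who complete the study: "date of end of Nucala – date of start of Nucala) + 1} / 365.25" (the opening brackets fall outside this quotation).
- Participants who enter follow-up: the same, but with 28 days added to the end date.

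For a missing date, both sections say: "If the date of end of Nucala is missing, the date of start of the last administration of Nucala + 28 days" will be used as the end date.

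SAP 6.2.2 sets the observation period separately, starting at the Week 0 dose. For those who stay in the study, it runs "to the stop date of Nucala +28 days for the participants who did not withdraw from study". Those who leave early have their own end point: "or the first treatment discontinuation date +28 days for the participants who withdraw from study". Its missing-date rule is: "When the last Nucala stop date is missing, the last Nucala start date will be imputed". SAP 6.2.3 agrees with it: "The duration of exposure to Nucala is calculated as (Nucala stop date – Nucala start date + 29"), with the same imputation.

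SAP 6.1.1 defines study completion as "A participant completed the observation period, which is scheduled for 96 weeks (approximately 2 years) at maximum". It defines early withdrawal as a category of its own: "A participant who was enrolled to this study but withdrew during the observation period".

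**The concern.** A rate is right only if events and time at risk cover the same dates. Here the period named for the rate and the offset in the model come from different rules, and they part in three places.

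1. Completers with a recorded end date get no 28-day tail in the offset, while 6.2.2 and 6.2.3 include one. The SAP does not say what the end date of Nucala is for someone who stays on the marketed drug. It could be the last injection, the Week 96 date or something else.
2. For follow-up entrants with a missing end date, the imputed date already contains 28 days and the follow-up formula adds 28 more.
3. Treated participants who withdraw without entering follow-up fit neither formula, although 6.2.2 gives them a window. A program that follows the text has no offset for them and leaves them out.

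At stake is the accuracy of two secondary effectiveness rates, and whether everyone in the TP contributes to them. No hypothesis test is involved.

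**Working it through.** The documents give no worked value for the offset, so there is no plan figure to reproduce. The check is date arithmetic.

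**Inputs.** The two formulas and their missing-date rule (SAP 4.3.1.2.3 and 4.3.1.2.4); the period and its missing-date rule (6.2.2, 6.2.3); dosing every 4 weeks and a 96-week maximum (SAP 1.2); about 120 participants and 10% expected dropout (SAP 5). Assumption: the start date is the Week 0 dose, as in 6.2.2.

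**First check: + 28 against + 29.** (stop + 28) − start + 1 = stop − start + 29. So 6.2.2 and 6.2.3 give the same length, and so does the follow-up formula when the date is recorded.

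**Length in days, case by case.**

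| Case | Offset in rate sections | 6.2.2 period | Difference |
|---|---|---|---|
| Completer, recorded end = Week 92 injection | 644 + 1 = 645 | 644 + 28 + 1 = 673 | −28 |
| Completer, recorded end = Week 96 date | 672 + 1 = 673 | 672 + 28 + 1 = 701 | −28 |
| Completer, last injection Week 92, end missing | 644 + 28 + 1 = 673 | 673 | 0 |
| Follow-up entrant, last dose Week 48, end recorded | 336 + 28 + 1 = 365 | 365 | 0 |
| Follow-up entrant, last dose Week 48, end missing | 336 + 28 + 28 + 1 = 393 | 365 | +28 |
| Withdrawal without follow-up | no formula | first discontinuation + 28 | not computable |

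**Completers.** With a Week 92 injection as end date, 673/645 = 1.043, so that participant's rate is 4.3% too high. With the Week 96 date, the offset of 673 days equals 96 × 7 + 1, the scheduled length, so there is no error against the schedule. Against 6.2.2 taken literally the gap is still 701/673 = 1.042.

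**Pooled effect against the scheduled length** (approximated by total person-time; assumed 108 completers and 12 follow-up entrants with last dose at Week 48). Reference person-time is 108 × 673 + 12 × 365 = 77,064 days.

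- No completer's end date is the last injection: 0%.
- Half are: 77,064/75,552 = 1.020.
- All are: 77,064/74,040 = 1.041. With 24 or 6 entrants instead of 12, this is 1.038 or 1.042.

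**Double count.** The individual offset is too long by 393/365 = 1.077 (last dose Week 48) or 141/113 = 1.248 (last dose Week 12). One such participant changes the pooled rate by 77,064/77,092 = 0.9996, and three by 77,064/77,148 = 0.9989. That is about −0.04% to −0.1%.

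**Withdrawals left out.** Their number is not given. As an illustration only, assume 3 or 12 of 120, a mean window of 337 days and 673 days for everyone else. The ratio of the rate without them to the rate with them is:

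- Same event rate: 1.
- Double the event rate: 79,752/80,763 = 0.987 for 3, and 76,728/80,772 = 0.950 for 12.
- Half the event rate: 1.006 and 1.027.

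**Scale.** Assume 0.2 events per year and dispersion 1. The mean count is 0.2 × 673/365.25 = 0.3685, and SE(log rate) = √((1/0.3685 + 1)/120) = 0.176. The 95% interval is then about −29% to +41%, and a 4.3% shift is ln(1.0434)/0.176 = 0.24 SE. Over 0.05 to 0.5 events per year and dispersion 0.5 to 2, it is 0.13 to 0.37 SE.

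**The case against.** The strongest reply is that the SAP is more coherent than it looks. The rate sections put the 28 days into the missing-date rule and leave them out of the completer formula. SAP 6.2.2 does the reverse. A completer on continuing treatment with no recorded end date gets 673 days either way. This is correct, so a reader who infers that the missing-date rules conflict in general would be wrong: they change the result only for follow-up entrants. It helps the other completers only if an ongoing end date is treated as missing, which the SAP does not say.

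Second, the double count is nearly empty. Follow-up is defined from a discontinuation date (6.1.1, 6.2.2), so an entrant would normally have one. This stands.

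Third, for withdrawals the derivation is already in 6.2.2 and has the same length as the follow-up formula. A sensible programmer would use it. But the rate sections do not call on it, while the section on corticosteroid dose (4.3.1.2.5) does tie its duration to the last day of the observation period.

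Fourth, a reader might infer that 6.2.2 is itself wrong because it can reach day 701. The documents do not support that: day 701 lies inside the Week 96 assessment window of SAP 6.2.4 (days 645 to 701). Cutting 6.2.2 at day 673 would also leave completers' adverse events on days 674 to 701 in no summary period, since follow-up applies only to those who discontinue.

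**Conclusion.** The point holds and is minor. For completers with a recorded end date, the offset is 28 days shorter than the 6.2.2 period. For follow-up entrants with a missing end date, 28 days are counted twice. Early withdrawals without follow-up have no offset.

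Measured against the scheduled 96 weeks, the pooled completer effect is 0% to about 4%, depending entirely on what is recorded as the end date. The documents do not settle this, so they do not support the stronger reading that the reported rates will be 4% too high. The double count moves the pooled rate by about 0.1% or less. The effect of omitting withdrawals is unknown; the figures above illustrate it and do not bound it. These scenarios are alternatives and should not be added together.

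The wording gap is certain, while the size rests on the stated assumptions. The endpoints are secondary and descriptive, no test is affected, and the shift is small against the likely confidence interval. The sample size does not depend on it.

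**What to change.** In SAP 4.3.1.2.3 and 4.3.1.2.4, replace the two formulas and the 28-day imputation with one person-time variable for every TP participant, including early withdrawals:

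- **Start:** the Week 0 dose, with the 6.2.2 fallback if that date is missing.
- **End:** the earlier of (a) the 6.2.2 end, that is, the first discontinuation date, or the last Nucala administration if treatment was not discontinued, plus 28 days; and (b) the participant's last study visit or contact.
- **Length:** end − start + 1.
- **Missing stop date:** the 6.2.2 imputation (last Nucala start date, before any re-treatment), so that 28 days are added only once.
- **Events:** count only those that fall within the same dates.

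Leave the 6.2.2 period unchanged for the adverse event summaries.

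The cost is a short SAP edit and one derived variable from data already collected. The downside is that rates may shift by a few percent from the interim report, which the final report should note.

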4.3.1.2.4. Annualized Rate of Emergency Room/Unscheduled Visit for EGPArelated Events

Endpoint

Annualized rate (event/year) of emergency room/unscheduled visit for EGPA-related events

Model Specification

The annualized rate of emergency room/unscheduled visit for EGPA-related events will be analyzed by using a negative binomial generalized linear model with logarithm of time as an offset variable, without covariate. The annualized rate and associated 95% CIs will be calculated by exponential transform the value of intercept term and associated 95% CIs estimated when the above model was applied. The annualized rate will be calculated in observation period and retrospective period independently.

Terms in the model:

- **Response**: number of recorded, on-treatment, emergency room/unscheduled visit for EGPA-related events experienced per participant.
- **Offset**: logarithm of treatment time in year

Observation period:

Treatment time in year for each participant will be calculated as:

Participants who complete the study:

{(date of end of Nucala – date of start of Nucala) + 1} / 365.25

Participants who enter follow-up period:

 $\{(date of end of Nucala + 28 - date of start of Nucala) + 1\} / 365.25$

For the raw value of calculation result, round off to two decimal places will be applied.

If the date of end of Nucala is missing, the date of start of the last administration of Nucala + 28 days will be imputed for the date of end of Nucala.

Retrospective period:

Treatment time in year for each participant will be calculated as:

48 / 52

SAS code:

proc genmod data = <dataset>;

```
model n_emv =
/ link=log dist=negbin offset=logfuinyears;
run;

data parm_est(keep= val rate rate_ll rate_ul);
set out_parm(where=(parameter='Intercept'));
format rate rate_ll rate_ul 8.2;
val= "annualized rate of emergency room/unscheduled visit for
EGPA-related events from negative binomial model without
covariate";
rate=exp(estimate);
rate_ll=exp(lowerwaldcl);
run;
```

where n_emv is the number of emergency room/unscheduled visit for EGPA-related events per participant in follow-up time, and logfuinyears is logarithm of the treatment time in years.

4.3.1.2.5. Average daily dose of OCS and Dosing categories

Endpoints

- Average daily dose (prednisolone-equivalent) of OCS
- The proportion of participants in the dosing categories relative to average daily OCS (prednisolone-equivalent)

Specification

To calculate the dose of OCS by prednisolone equivalent, multiply by the following coefficients.

Generic name	GSK Drug Code	Prednisolone equivalent value	Coefficient
Hydrocortisone	00028601	20	0.250
Hydrocortisone succinate	00028602	20	0.250
Cortisone acetate	00014602	25	0.200
Prednisolone	00016201	5	1.000
Prednisolone succinate	00016203	5	1.000
Methylprednisolone	00049601	4	1.250
Methylprednisolone succinate	00049602	4	1.250
Triamcinolone	00031901	4	1.250
Triamcinolone acetonide	00031902	4	1.250
Dexamethasone	00016001	0.75	6.667
Dexamethasone phosphate	00016002	0.75	6.667
Paramethasone acetate	00066402	2	2.500
Betamethasone	00008501	0.75	6.667
Betamethasone phosphate	00008502	0.75	6.667

Average daily dose of OCS for each participant will be calculated by 12-weekly periods and the retrospective period as:

Total dosage of OCS (mg) / Total duration of administration of OCS (day) Total duration of administration is defined as:

• By 12-weekly period

Last date of each period - later date of (first date of each period or start date of OCS) +1

12-weekly period is described in Section 6.2.4. If OCS is administered and then OCS is no longer required on the last date of each period, 0 mg will be imputed.

• Retrospective period

Last date of retrospective period–later date of (start date of retrospective period or start date of OCS) + 1

Average daily OCS in the retrospective period will be calculated if a participant uses OCS in the retrospective period, otherwise average daily OCS will be 0 mg. If OCS is administered and then OCS is no longer required on the last date of the retrospective period, 0 mg will be imputed.

Over observation period

Last day of observation period (Week 48 for interim analysis, if participant is on-going on observation period) - later date of (date of dose of Nucala at Week 0 or start date of OCS) +1.

If the date of dose of Nucala at Week 0 is missing, the latest available date between the date of screening visit and the date of visit at week 0 will be used for calculation of observation period. If OCS is administered and then OCS is no longer required during the observation period, 0 mg will be imputed.

When more than one OCS is administered to a participant in the same period, the sum of OCS doses will be used as daily OCS dose.

Summary statistics of average daily dose of OCS will be calculated by the retrospective period and 12-weekly periods. Average daily dose of OCS percent change from Week 0 and from retrospective period will also be summarized by 12-weekly periods. A box plot and a line plot of the median average daily dose of OCS will be produced.

Average daily dose of OCS percent change from Week 0 and from retrospective period is calculated as:

Percent change = ((average daily dose of OCS at each 12-weely period - average daily dose of OCS at Week 0 (or retrospective period))/ average daily dose of OCS at Week 0 (or retrospective period))*100 (%)

The frequency and percentage of participants in the following dosing categories relative to average daily OCS will be summarized by the retrospective period and 12-weekly periods. The denominator of the frequency is the TP. A line plot of the percentage of patients with 0 mg/day of average daily OCS will be presented.

Daily OCS dosing category:

- 0 mg/day, 0 mg/day < \leq 4.0 mg/day, 4.0 mg/day < \leq 7.5 mg/day, 7.5 mg/day <
- $0 \text{ mg/day} \le 2.0 \text{ mg/day}, 2.0 \text{ mg/day} \le 4.0 \text{ mg/day}$

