# 4.6. Secondary and Exploratory Analyses

The secondary and exploratory analyses will be performed for the TP population. All endpoints will be summarised by using appropriate descriptive statistics.

The summary table will be also produced by the observation period and the follow-up period, respectively.

The endpoints selected for secondary and exploratory analyses are listed below by objective:

To investigate the long-term effectiveness of Nucala in adult patients with EGPA in Japan

- Proportion of participants with clinical symptoms as assessed by 9 organ-systems (i.e. systemic, skin, mucous membranes/eyes, ears/nose/throat, chest, cardiovascular, abdominal, renal, nervous system) for the observation period of 96 weeks.
- Proportion of participants with EGPA relapse for the observation period of 96 weeks.
   EGPA relapse is defined as any of the following with worsening EGPA.\*
  - 1) Increased dose of OCS.
  - 2) Initiation/increased dose of immuno-suppressive agents.\*\*
  - 3) EGPA treatment with hospitalization.
  - \* Worsening of EGPA: new onset of EGPA symptoms or worsening of existing symptoms.
  - \*\* Immunosuppressive agents: If the dose of immunosuppressive agents increases for the same formulation or if the number of immunosuppressive agents increases for EGPA treatment.
- Annualized rate (event/year) of hospitalization for EGPA-related events

213684

 Annualized rate (event/year) of emergency room/unscheduled visit for EGPA-related events

The annualized rate of hospitalization for EGPA treatment will be analysed by using a negative binomial generalized linear model with logarithm of time as an offset variable, from which the estimated event per year and associated 95% CIs will be calculated.

- Average daily dose (prednisolone-equivalent) of OCS over 96 weeks
- The proportion of subjects in the dosing categories\* relative to average daily OCS (prednisolone-equivalent) over 96 weeks
  - \* Zero, >0 to ≤4.0 mg/day, >4.0 to ≤7.5 mg/day, >7.5 mg/day

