4.3. Secondary Endpoint(s) Analyses

4.3.1. Secondary endpoint(s)

4.3.1.1. Definition of endpoint(s)

The secondary endpoints are as follows:

- Proportion of participants with clinical symptoms as assessed by 9 organ-systems (i.e. systemic, skin, mucous membranes/eyes, ears/nose/throat, chest, cardiovascular, abdominal, renal, nervous system)
- Proportion of participants with EGPA relapse
- Annualized rate (event/year) of hospitalization for EGPA-related events
- Annualized rate (event/year) of emergency room/unscheduled visit for EGPA-related events
- Average daily dose (prednisolone-equivalent) of oral corticosteroid (OCS) over the observation period
- The proportion of participants in the dosing categories^{*} relative to average daily OCS (prednisolone-equivalent) over the observation period
 * 0 mg/day, 0 mg/day < ≤ 4.0 mg/day, 4.0 mg/day < ≤ 7.5 mg/day, 7.5 mg/day <

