4.6.3. EGPA Remission

EGPA remission is defined as each of the combinations of the clinical symptoms as assessed by 9 organ-systems and average daily dose of OCS.

- Participants with no clinical symptoms as assessed by 9 organ-systems
- Participants with no "worsening" clinical symptoms as assessed by 9 organ-systems
- Participants with average daily dose of OCS in $\leq 4.0 \text{ mg/day}$

• Participants with average daily dose of OCS in 0 mg/day

The frequency and percentage of participants in EGPA remission by EGPA remission period will be summarized. Line plots by EGPA remission period will also be produced for the proportion of participants with average daily dose of OCS in ≤ 4.0 mg/day and in 0 mg/day. The plots will be displayed for the participants with no clinical symptoms as assessed by 9 organ-systems and no "worsening" clinical symptoms separately.

The period for EGPA remission is defined as follows:

EGPA remission period	Clinical symptoms as assessed by 9 organ- systems	Average daily dose of OCS
Week 12/Weeks 9-12	Week 12	Weeks 9-12
Week 24/Weeks 21-24	Week 24	Weeks 21-24
Week 36/Weeks 33-36	Week 36	Weeks 33-36
Week 48/Weeks 45-48	Week 48	Weeks 45-48
Week 60/Weeks 57-60	Week 60	Weeks 57-60
Week 72/Weeks 69-72	Week 72	Weeks 69-72
Week 84/Weeks 81-84	Week 84	Weeks 81-84
Week 96/Weeks 93-96	Week 96	Weeks 93-96

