6.2.4. Assessment Window

The assessment time points defined below are used in the analysis. When calculating the assessment date, the visit closest to the specified date is used, and if the period from the specified date is the same, the latest visit is used.

Assessment window will be applied to early withdrawal dates. If participants prematurely withdraw from the study and do not have the visit date of Week 96, 673 days after Week 0 will be imputed to missing visit date of Week 96.

If the derived data based on the study day is included in the range of period, the corresponding week is assigned as below and will be used for analysis.

Assessment time points	Specified data	Window	Period	iod (day)	
Assessment time points	specified date	(±day)	From	to	
Week 0	1	-	-28	1	
Week 12	85	28	57	113	
Week 24	169	28	141	197	
Week 36	253	28	225	281	
Week 48	337	28	309	365	
Week 60	421	28	393	449	
Week 72	505	28	477	533	
Week 84	589	28	561	617	
Week 96	673	28	645	701	

The following shows the assessment window for the follow-up period.

Assessment time noint	Specified data	Window	Period (day)	
Assessment time point	specified date	(±day)	From	to
Follow Week 0	1	-	-	1
Follow Week 12	85	28	57	113
Follow Week 24	169	28	141	197
Follow Week 36	253	28	225	281

Assessment time point	Specified date	Window	Period (day)	
		(±day)	From	to
Follow Week 48	337	28	309	365
Follow Week 60	421	28	393	449
Follow Week 72	505	28	477	533
Follow Week 84	589	28	561	617
Follow Week 96	673	28	645	701

OCS dose and immuno-suppressive therapy is recorded on a daily basis and will be averaged into 12-weekly periods as below. If the date of dose of Nucala at Week 0 is missing, the latest available date between the screening visit date and the Week 0 visit date will be used for the start date of the observation period.

12-weekly period	First date	Last date
Weeks 9-12	Nucala start date at Week 0 +	Nucala start date at Week 0 +
	56 days	84 days
Weeks 21-24	Nucala start date at Week 0 +	Nucala start date at Week 0 +
	140 days	168 days
Weeks 33-36	Nucala start date at Week 0 +	Nucala start date at Week 0 +
	224 days	252 days
Weeks 45-48	Nucala start date at Week 0 +	Nucala start date at Week 0 +
	308 days	336 days
Weeks 57-60	Nucala start date at Week 0 +	Nucala start date at Week 0 +
	392 days	420 days
Weeks 69-72	Nucala start date at Week 0 +	Nucala start date at Week 0 +
	476 days	504 days
Weeks 81-84	start date at Week $0 + 560$	Nucala start date at Week 0 +
	days	588 days

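### The average daily OCS dose leaves out OCS-free days before a start inside the period but keeps those after a stop as 0 mg, so it is inflated for participants who start OCS within a period

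*SAP*

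**What the plan says.** Protocol 4.6 lists as an endpoint "Average daily dose (prednisolone-equivalent) of OCS over 96 weeks". SAP 1.1 repeats the 96-week wording, and SAP 4.3.1.1 gives "Average daily dose (prednisolone-equivalent) of oral corticosteroid (OCS) over the observation period", together with the proportion of participants in four dosing categories based on that average.

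SAP 4.3.1.2.5 calculates the average as total OCS dose in mg divided by a duration of administration in days. For the 12-weekly periods that duration is "Last date of each period - later date of (first date of each period or start date of OCS) +1". For the retrospective period it is counted from the "later date of (start date of retrospective period or start date of OCS) + 1". For the whole observation period the start is the later of the Week 0 Nucala dose and the OCS start. In all three cases the count runs to the last day of the period. Days after stopping remain in the count; for the whole period the text reads "If OCS is administered and then OCS is no longer required during the observation period, 0 mg will be imputed", and the other two periods have a parallel sentence.

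SAP 6.2.4 describes the averaging differently: "OCS dose and immuno-suppressive therapy is recorded on a daily basis and will be averaged into 12-weekly periods as below", followed by windows with fixed first and last dates.

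**The concern.** The two ends of the denominator are treated differently. OCS-free time before a start is removed, and OCS-free time after a stop is retained. An average over the period would keep both, and an average while on OCS would drop both. The SAP quantity is neither whenever the OCS start date falls inside the period, and it does not match the fixed-date averaging in SAP 6.2.4.

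For those participants the value depends on when in the period OCS was started as well as on how much was taken. This reaches several outputs:

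- the dosing categories, which are a listed secondary endpoint;
- percent change from the retrospective period (SAP 4.3.1.2.5);
- remission, where "EGPA remission is defined as each of the combinations of the clinical symptoms as assessed by 9 organ-systems and average daily dose of OCS" and one component is an average of at most 4.0 mg/day;
- the subgroup defined by OCS dose, and the OCS endpoint within the other subgroups (SAP 4.6.4).

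The two biases run in opposite directions. Inflation on study moves participants to higher categories and makes them fail the remission threshold, which works against Nucala. Inflation in the 12 weeks before first Nucala raises the reference and exaggerates the reported reduction. The planned summaries give no means of separating the two, and SAP 4.3.1.3 plans no sensitivity analysis.

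**Working it through.** The documents give no numerical OCS result, so there is no figure to reproduce. The check applies the SAP rule and the all-days average to the same courses.

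**Inputs from the documents**
- 12-weekly window: Week 0 date + 56 to + 84 days, and so on (SAP 6.2.4), i.e. 84 − 56 + 1 = 29 days.
- Retrospective period: 12 weeks = 84 days (SAP 4.1.2).
- Week 96 is Day 673 (SAP 6.2.4). The observation period runs to the Nucala stop date + 28 days (SAP 6.2.2), so it could end at Day 673 + 28 = 701.
- Categories: 0; >0 to 4.0; >4.0 to 7.5; >7.5 mg/day.

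**Assumed:** the OCS doses and dates in the examples. I read the 0 mg imputation as 0 mg on each day after stopping.

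**Formulas**
- SAP rule: total mg / (last day − later of first day and OCS start + 1).
- Average over the period: total mg / (last day − first day + 1).
- Inflation = days in period / days from OCS start to period end, counting the last day.

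| Period | Days from OCS start to end | Inflation |
|---|---|---|
| 29-day window | 25 | 29/25 = 1.16 |
| 29-day window | 10 | 29/10 = 2.9 |
| 29-day window | 5 | 29/5 = 5.8 |
| 84-day retrospective | 70 | 84/70 = 1.2 |
| 84-day retrospective | 28 | 84/28 = 3.0 |
| 84-day retrospective | 14 | 84/14 = 6.0 |

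**Example 1. Same exposure, different start day.** 10 mg/day for 5 days of a 29-day window is 50 mg in total. The average over the period is 50/29 = 1.72 mg/day in every row.

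| OCS starts on window day | SAP rule (mg/day) | Category |
|---|---|---|
| 1 | 50/29 = 1.72 | >0 to 4.0 |
| 20 | 50/10 = 5.0 | >4.0 to 7.5 |
| 25 | 50/5 = 10.0 | >7.5 |

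**Example 2. Start late versus stop early.** 10 mg/day for 7 days of the window: 70/7 = 10.0 if they are the last 7 days, 70/29 = 2.41 if they are the first 7. The average over the period is 2.41 in both cases.

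**Example 3. Retrospective reference.** 30 mg/day for the last 14 of 84 days is 420 mg. SAP rule: 420/14 = 30 mg/day. Average over the period: 420/84 = 5 mg/day. If the participant later averages 5 mg/day, the change is (5 − 30)/30 = −83% under the SAP rule and (5 − 5)/5 = 0% on the period average.

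**Example 4. Whole observation period.** 30 mg/day for 14 days from Day 589 is 420 mg.
- Period ends Day 673: 420/(673 − 589 + 1) = 420/85 = 4.94, against 420/673 = 0.62. The category shifts.
- Period ends Day 701: 420/(701 − 589 + 1) = 420/113 = 3.72, against 420/701 = 0.60. The category does not shift.

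**Control.** For 5 mg/day taken from before the period to its end, both rules give 5.0. Only a start inside the period produces a difference.

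**The case against.** The strongest reply is that few participants may be affected. The eight windows cover 8 × 29 = 232 of 673 days, about 34%, and only an OCS start inside a window distorts that window's value. If the OCS start date means the first start, each participant can be affected in at most one window. Participants have had at least 96 weeks of Nucala and were inadequately controlled on earlier therapy, so first-ever OCS starts on study may be uncommon. The plots use medians, which a few inflated values move little. Percent change is also reported from Week 0, which retrospective inflation does not touch. Profile plots of daily OCS dose and medication listings let a reader see individual courses. In Example 3 one may argue that 30 mg/day better describes the dose when Nucala began. The endpoint is secondary and descriptive, and Protocol 5 already urges caution about effectiveness.

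Much of this stands as a limit on reach. None of it makes the rule compute the named endpoint. If the dose at Nucala start is of interest, it is a different quantity and should be labelled as such. In a study without hypothesis tests the descriptive estimates are the output, so they should match their labels. Category percentages, unlike medians, count every misplaced participant.

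The 0 mg sentence could instead mean that the whole period's value is set to 0 after a stop. That would change Examples 1, 2 and 4 and would also affect the 0 mg/day category, but it would make starters and stoppers still more unequal.

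**Conclusion.** The concern holds and should be fixed. As written, the rule gives the wrong value for a listed secondary endpoint and its dosing categories whenever OCS starts inside the period being averaged. In the cases shown the inflation is 1.16-fold to 5.8-fold in a 29-day window and 1.2-fold to 6-fold in the retrospective period. It grows as the start moves towards the end of the period.

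This rests on reading the 0 mg imputation as applying to days after stopping, and the example doses and dates are illustrative. New starters are affected on any reading. Restarters are affected only if the OCS start date means the current record, which SAP 4.3.1.2.5 does not say. OCS already ongoing at period start is unaffected and, on the reading used here, so is the 0 mg/day category. The number of participants affected cannot be computed from the documents.

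Two lesser gaps sit in the same section; the conclusion does not depend on them. The reporting text says "Summary statistics of average daily dose of OCS will be calculated by the retrospective period and 12-weekly periods" and does not name the whole-observation average or its categories, although the general statement in SAP 4.3.1.2 that all endpoints will be summarised partly covers this. Percent change is undefined when the reference is 0 mg, a value the SAP assigns to participants with no retrospective OCS.

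**What to change.** In SAP 4.3.1.2.5, for the 12-weekly, retrospective and whole-observation averages alike, set the denominator to last day − first day + 1 of the period, with 0 mg on every OCS-free day before, between and after courses. End the observation period as defined in SAP 6.2.2, or at the end of the participant's data if earlier. State that 4.3.1.2.5 and 6.2.4 describe the same daily average. With this denominator the meaning of the OCS start date no longer matters for restarts.

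In the same edit, name the whole-observation average and its four categories in the table list, and report absolute change in mg/day beside percent change so that participants with a 0 mg reference are included.

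The cost is one formula and a few table rows, using doses already recorded daily. OCS summaries already produced for the 48-week interim analysis would have to be re-run so that interim and final results are comparable. No data collection or treatment rule changes.
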